CCSS	Central Corneal Staining Score
CFB	Change from Baseline
CI	Confidence Interval
CS	Clinically Significant
eCRF	Electronic Case Report Form
EDS	Eye Dryness Score
ETDRS	Early Treatment of Diabetic Retinopathy Study
ICH	International Conference on Harmonisation
IOP	Intraocular Pressure
IP	Investigational Product
IRT	Interactive Response Technology
ITT	Intent-to-Treat
LOCF	Last Observation Carried Forward
logMAR	Logarithm of the Minimum Angle of Resolution
LS	Least Squares
MCMC	Markov Chain Monte Carlo
MedDRA	Medical Dictionary for Regulatory Activities
MMRM	Mixed model repeated measures
NCS	Not Clinically Significant
OD	Oculus dexter (Right Eye)
OS	Oculus sinister (Left Eye)
OSDI®	Ocular Surface Disease Index®
PDF	Portable Document Format
PMM	Pattern-Mixture Model
PP	Per Protocol
PT	Preferred Term
RTF	Rich Text Format
SAE	Serious Adverse Event
SAP	Statistical Analysis Plan
SD	Standard Deviation
SDC	Statistics & Data Corporation
SE	Standard Error
SOC	System Organ Class
TEAE	Treatment-Emergent Adverse Event

Abbreviation	Definition
TE-SAE	Treatment-Emergent Serious Adverse Event
TFBUT	Tear Film Break-Up Time
VA	Visual Acuity
VAS	Visual Analog Scale
WHODrug	World Health Organization Drug Dictionary

1. Introduction

The purpose of this statistical analysis plan (SAP) is to describe the planned analyses and reporting for protocol HL036-DED-US-P302 Version 4.0, dated 22-JUN-2022

This SAP is being written with due consideration of the recommendations outlined in the most recent International Conference on Harmonisation (ICH) E9 Guideline entitled Guidance for Industry: Statistical Principles for Clinical Trials, E9(R1) Statistical Principles for Clinical Trials: Addendum: Estimands and Sensitivity Analysis in Clinical Trials, and the most recent ICH E3 Guideline entitled Guidance for Industry: Structure and Content of Clinical Study Reports.

This SAP describes the data that will be analyzed and the subject characteristics, efficacy, and safety assessments that will be evaluated. This SAP provides details of the specific statistical methods that will be used. The statistical analysis methods presented in this document will supersede the statistical analysis methods described in the clinical protocol. If additional analyses are required to supplement the planned analyses described in this SAP they may be completed and will be identified in the clinical study report.

2. Study Objectives

The objective of this study is to compare the safety and efficacy of Tanfanercept Ophthalmic Solution 0.25% to placebo for the treatment of the signs and symptoms of dry eye.

2.1 Primary Variables

The primary efficacy variables of the study are:

- Central corneal staining score (CCSS; sign), mean change from baseline (V2) to Day 57 ± 3 (V6, Week 8)
- Eye dryness score on Visual Analog Scale (EDS-VAS; symptom), mean change from baseline (V2) to Day 57 ± 3 (V6, Week 8)

2.2 Secondary Variables

The secondary efficacy variables include the following:

- Fluorescein staining (Ora Calibra® scale) by region: central, superior, inferior, temporal, nasal, corneal sum, conjunctival sum, and total staining
- Conjunctival lissamine green staining (Ora Calibra® scale) by region: central, superior, inferior, temporal, nasal, corneal sum, conjunctival sum, and total staining
- Conjunctival redness
- Unanesthetized Schirmer's Test
- Tear film break-up time (TFBUT)
- Visual Analog Scale (VAS) (reported symptoms include burning/stinging, itching, foreign body sensation, blurred vision, eye dryness, photophobia, and pain)
- Ocular Surface Disease Index® (OSDI®)

- Ora Calibra® Ocular Discomfort Scale
- Ora Calibra® Ocular Discomfort & 4-Symptom Questionnaire

2.3 Safety Variables

The safety variables include the following:

- Adverse event (AE) query
- Visual acuity (VA)
- Slit-lamp evaluation
- Intraocular Pressure (IOP)
- Dilated fundoscopy
- Immunogenicity to Tanfanercept Ophthalmic Solution 0.25% in serum

2.4 Other Variables

The other variables include the following:

- Ora Calibra® Drop Comfort Scale
- Ora Calibra® Drop Comfort Questionnaire

2.5 Statistical Hypotheses

The statistical hypotheses are stated in terms of two-sided hypotheses, although statistical inference will be one-sided, with the direction of interest in the differences in treatment group means as stated in [Section 13.1](#). The primary endpoints will be tested in a hierarchical fixed sequence in the following order.

H_{01} : There is no difference between Tanfanercept Ophthalmic Solution 0.25% and placebo in the change from baseline (Visit 2 [Day 1]) of the CCSS at Day 57 \pm 3 (Visit 6, Week 8) in the ITT Population, using the Ora Calibra® scale (Ex. H_{01} : $\mu_t = \mu_p$).

H_{A1} : The change from baseline (Visit 2 [Day 1]) of the CCSS at Day 57 \pm 3 (Visit 6, Week 8) using the Ora Calibra® scale is not equal with Tanfanercept Ophthalmic Solution 0.25% than with placebo in the ITT Population (Ex. H_{A1} : $\mu_t \neq \mu_p$).

H_{02} : There is no difference between Tanfanercept Ophthalmic Solution 0.25% and placebo in the change from baseline (Visit 2 [Day 1] of the EDS on VAS at Day 57 \pm 3 (Visit 6, Week 8) in the ITT Population (Ex. H_{02} : $\mu_t = \mu_p$).

H_{A2} : The change from baseline (Visit 2 [Day 1]) of the EDS on VAS is not equal with Tanfanercept Ophthalmic Solution 0.25% than with placebo at Day 57 \pm 3 (Visit 6, Week 8) in the ITT Population (Ex. H_{A2} : $\mu_t \neq \mu_p$).

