10.2 Statistical Hypotheses

The statistical hypotheses are stated in terms of one-sided hypotheses, although statistical testing will be two-sided at a significance level of 0.05. The primary endpoints will be tested in a hierarchical fixed sequence in the following order:

H_{01} : There is no difference in change from baseline (V2) of CCSS at Day 57 ± 3 (V6, Week 8) in the study eye between tanfanercept ophthalmic solution 0.25% and placebo ophthalmic solution in the ITT population (Ex. H_{01} : $\mu_t = \mu_p$).

H_{A1} : The change in baseline (V2) of CCSS at Day 57 ± 3 (V6, Week 8) in the study eye is less with tanfanercept ophthalmic solution 0.25% than placebo ophthalmic solution in the ITT population (Ex. H_{A1} : $\mu_t < \mu_p$).

H_{02} : There is no difference in change from baseline (V2) of EDS from VAS at Day 57 ± 3 (V6, Week 8) between tanfanercept ophthalmic solution 0.25% and placebo ophthalmic solution in the ITT population (Ex. H_{02} : $\mu_t = \mu_p$).

H_{A2} : The change in baseline (V2) of EDS from VAS at Day 57 ± 3 (V6, Week 8) is less with tanfanercept ophthalmic solution 0.25% than placebo ophthalmic solution in the ITT population (Ex. H_{A2} : $\mu_t < \mu_p$).

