 - Non-optimal compliance is ignored. Measures will be analyzed regardless of treatment compliance. [treatment policy strategy]
 - Use of prohibited concomitant medications is ignored. Measures obtained after use of prohibited concomitant medications will be analyzed. [treatment policy strategy]
 - Withdrawal or missed assessments for any reason. Missing values will be removed, following the trimmed means methodology laid out in Permutt T, Li F. [hypothetical strategy]. The trimmed means strategy is as follows:
 - Using an analysis of covariance (ANCOVA), a linear model is fit to the data with treatment as factor and baseline value as covariate. The beta coefficient for treatment is discarded and only the Y (outcome) value, the beta coefficient for baseline score, and X (baseline score) are considered. $Y - \beta(X)$ is then calculated for each subject for the purpose of ranking.
 - Next, the proportions of subjects with missing values in the control and treatment arms are identified. The greater proportion of the two arms is then used as the percentile floor in which observations must be better. Those observations that are not better than the floor are trimmed (removed). Missing values are included in the calculation of the percentile floor value as values worse than the percentile.
 - After trimming is done, MMRM is used on the two analysis sets to find an observed treatment effect. The MMRM model will be based on the final model as described in [Section 13.1.1](#). To determine the p-value and 95% CI, 10,000 permutations of the data will be run and the trimming methodology will be repeated. The number of permutation datasets that result in an effect size greater than the observed effect size divided by the number of permutations will be the p-value. The 95% CI will be calculated using the 2.5th and 97.5th percentiles of the permutation distribution.
- Population-level summary:
 - Difference in the mean CFB in EDS-VAS at Day 57 ± 3 between Tanfanercept and placebo in the ITT population.

3. Study Design and Procedures

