8.4 Data Analysis Conventions

All data analyses will be performed after the study is completed and the database has been locked and released for unmasking. Statistical programming and analyses will be performed using SAS® Version 9.4 or higher. Output will be provided in RTF (rich text format) for tables, listings, and figures using landscape orientation. All study data will be listed by subject, treatment, and visit (as applicable) based on all enrolled subjects unless otherwise specified.

All summaries will be presented by treatment group and visit where appropriate, unless otherwise specified. Listings will be presented for all data collected on the eCRFs, sorted by subject id number and visit.

Summaries for continuous and ordinal variables will include the number of observations (n), arithmetic mean, SD, median, minimum, and maximum. Minima and maxima will be reported with the same precision as the raw values; means and medians will be presented to one additional decimal place than reported in the raw values. Standard deviations will be presented to two additional decimal places than reported in the raw values. Summaries for discrete variables will include frequency counts and percentages. All percentages will be rounded to one decimal place (i.e., XX.X%).

All statistical tests will be two-sided with a significance level of 0.05 ($\alpha = 0.05$) unless otherwise specified. Confidence intervals (CI) will be two-sided at 95% confidence levels where appropriate. All p-values will be rounded to four decimal places; p-values less than 0.0001 will be presented as "<0.0001"; p-values greater than 0.9999 will be presented as ">0.9999."

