8.5 Adjustments for Multiplicity

Hierarchical fixed sequence testing will be used to maintain the type I error rate. The primary analysis will first test the difference in CFB (Day 1) of CCSS in the study eye at Day 57 in the ITT population using the primary estimand. If the test of the difference between treatment groups is statistically significant at the two-sided alpha = 0.05 level in favor of Tanfanercept, then the study will be considered a success, Tanfanercept will be declared to be superior to placebo in the change from baseline (Day 1) of CCSS at Day 57, and the difference in the change from baseline (Day 1) of EDS at Day 57 will then be tested at the two-sided alpha = 0.05 level in the ITT population.

If, in addition to a statistically significant test of the difference in change from baseline (Day 1) of CCSS in the study at Day 57 in favor of Tanfanercept, the test of the difference in the change from baseline (Day 1) of EDS at Day 57 in the ITT population with the primary estimand is also statistically significant in favor of Tanfanercept, then Tanfanercept will be declared superior to placebo in both the change from baseline (Day 1) of CCSS and the change from baseline (Day 1) of EDS at Day 57.

Secondary efficacy analyses will not be type-I error controlled and will be considered hypothesis generating.

9. Disposition

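### SAP 2.5 calls primary inference one-sided and gives no alpha, against the two-sided 0.05 success rule in SAP 8.5 and the protocol; separately, the SAP 2.6 permutation p-value leaves its tail undefined

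*SAP*

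**What the plan says.** **Sidedness of the primary tests**

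- SAP 2.5 introduces the hypotheses for CCSS and EDS with: "The statistical hypotheses are stated in terms of two-sided hypotheses, although statistical inference will be one-sided". The rest of the sentence refers to SAP 13.1 for the direction of interest. No significance level is given. The alternatives below it are two-sided; for CCSS, the change "is not equal with Tanfanercept Ophthalmic Solution 0.25% than with placebo in the ITT Population".
- SAP 8.5 sets the success rule. If the CCSS test is "statistically significant at the two-sided alpha = 0.05 level in favor of Tanfanercept, then the study will be considered a success", and EDS is then tested at the same two-sided level.
- SAP 8.4 sets the general convention: "All statistical tests will be two-sided with a significance level of 0.05". It allows exceptions stated elsewhere.
- Protocol 10.2 reads: "The statistical hypotheses are stated in terms of one-sided hypotheses, although statistical testing will be two-sided at a significance level of 0.05". Protocol 10.4.1 and 10.4.4 also say two-sided 0.05.
- SAP 1 makes the SAP's methods prevail over the protocol's. SAP 18 declares no changes from the protocol's analyses.

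**Permutation p-value (Estimand 2)**

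- SAP 2.6 defines the p-value as follows: "The number of permutation datasets that result in an effect size greater than the observed effect size divided by the number of permutations". It does not say whether the effect is signed or absolute.
- SAP 13.1 defines the treatment difference as active minus placebo, with a negative value favouring active.
- Protocol 10.4.5 promises a two-sided exact p-value from the trimmed-means permutation test.

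**The concern.** Sidedness is part of the decision rule for both primary endpoints. The SAP states it one way in the hypotheses section and the opposite way in the multiplicity section.

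The usual tie-breakers do not remove the conflict. The protocol cannot settle it, because the SAP takes precedence on methods. SAP 8.4 leaves room for exceptions, and SAP 2.5 could be taken as one. Since SAP 18 declares no changes, SAP 2.5 is either a drafting error or an undeclared change, and either needs correcting. SAP 13.1.1 does not help for the main test: it calls the supportive t-test p-values two-sided but attaches no sidedness to the MMRM p-value, which protocol 10.4.5 does call two-sided.

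At stake is how a borderline result would be read. EDS is the likelier place for one, because the protocol synopsis says the study is powered on the sign endpoint. If the sentence is left as it is, the choice of reading could be argued after unmasking.

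The permutation p-value is a separate gap. It bears on a primary test only if EDS missingness is both imbalanced (Fisher's exact p below 0.05) and at least 10% overall, the trigger in SAP 2.6.

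**Working it through.** **Step 1. The texts side by side**

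| Place | Hypotheses | Test or inference | Level |
|---|---|---|---|
| Protocol 10.2 | one-sided (less than) | two-sided | 0.05 |
| Protocol 10.4.1, 10.4.4 | – | two-sided | 0.05 |
| SAP 2.5 | two-sided (not equal) | one-sided | none given |
| SAP 8.4 | – | two-sided, exceptions allowed | 0.05 |
| SAP 8.5 (success rule) | – | two-sided, in the drug's favour | 0.05 |

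SAP 2.5 is the only outlier, and it mirrors protocol 10.2 with the two terms exchanged. Neither document states a one-sided level, whether 0.05 or 0.025.

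**Step 2. Do the plan's power figures show which sidedness was used?**

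SAP 5 gives 99.4% power with 135 evaluable per group and 98.7% with 119, on the same assumptions and a significance level of 0.05. The difference and SD are redacted. I therefore solved for the standardised difference d that gives 99.4% at 135 per group (noncentral t) and applied it at 119, taken as printed.

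- Two-sided 0.05: d = 0.546, power at 119 = 98.73%.
- One-sided 0.05: d = 0.507, power at 119 = 98.80%.

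The 99.4% is itself rounded. Letting it run from 99.35% to 99.449% gives 98.65% to 98.82% (two-sided) and 98.71% to 98.88% (one-sided) at 119. Both ranges contain values that print as 98.7%. The stated power is reproduced under the two-sided rule but does not rule out the other.

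**Step 3. False-positive rate in the drug's favour**

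Rate = 1 − Φ(z), where z is the critical value in the favourable direction.

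| Rule | Critical z | Rate in favour |
|---|---|---|
| Two-sided 0.05, claim only in favour (SAP 8.5) | 1.960 | 0.05/2 = 0.025 |
| One-sided 0.025 | 1.960 | 0.025 |
| One-sided 0.05 | 1.645 | 0.050 |

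Only the third row changes anything. Under it:

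- Favourable results with |z| between 1.645 and 1.960, that is two-sided p between 0.05 and 0.10, would become successes.
- The smallest significant difference at 119 per group would fall from 1.960 × √(2/119) = 0.254 SD to 1.645 × √(2/119) = 0.213 SD.
- With d = 0.546, power would rise from 98.7% to 99.5% at 119 per group and from 99.4% to 99.8% at 135.

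**Step 4. The permutation p-value**

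The p-value is the count of permuted effects greater than the observed effect, divided by 10,000. There are three possible readings.

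- *Signed, active minus placebo (the SAP 13.1 scale).* Benefit is negative, so nearly all permuted effects exceed a clearly beneficial one. At z = −1.960 about 97.5% do, so p is about 0.975. This is the wrong tail.
- *Signed, with benefit recoded as positive.* This is one-tailed. In a simplified null simulation (119 per group, no trimming or MMRM, 2,000 trials of 1,000 permutations), p fell below 0.05 in the drug's favour in 4.5% of trials (Monte Carlo SE about 0.5 points). The SAP does not state this recoding.
- *Absolute.* This is two-sided. In the same simulation, 2.1% of trials were significant in the drug's favour (SE about 0.3 points), consistent with 2.5%.

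Only the absolute reading matches the two-sided exact p-value of protocol 10.4.5, and SAP 2.6 does not say that it is meant.

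**The case against.** The strongest reply is that the success rule is stated correctly where it counts. SAP 8.5 decides success and says two-sided 0.05, while SAP 2.5 gives no alpha, critical value or criterion. SAP 2.5 also has a reading that agrees with SAP 8.5: its alternatives are two-sided, and its reference to SAP 13.1 points only to the sign convention. One-sided inference may then mean no more than that superiority is claimed in one direction. SAP 18 and the protocol point the same way. Giving the SAP precedence over the protocol does not help the one-sided reading much, because SAP 8.5 is part of the SAP.

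Most of this stands. A reader might infer that the SAP has adopted a one-sided 0.05 test and so doubled the type I error. The documents do not support that: it joins the word one-sided from SAP 2.5 to a 0.05 that SAP 8.4 and 8.5 attach to two-sided tests.

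A reader might also infer that the permutation p-value is a one-tailed test that eases the hurdle for the drug. That is not supported either. The text says neither signed nor absolute, the interval beside it uses the 2.5th and 97.5th percentiles, and the literal signed count works against a benefit. The 4.5% in the simulation needs a recoding that the SAP does not make.

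What the reply does not remove is the contradiction. SAP 2.5 says one-sided of the inference on the same two tests that SAP 8.5 calls two-sided, and agreement depends on interpretation.

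**Conclusion.** SAP 2.5 is wrong as written and should be corrected before unmasking. It contradicts SAP 8.4 and 8.5 and protocol 10.2, 10.4.1 and 10.4.4 on the sidedness of the primary tests. An inverted copy of protocol 10.2 is the probable origin; that is an inference from the mirrored wording and the no-changes statement in SAP 18.

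The size is conditional. Under SAP 8.5, or with one-sided testing at 0.025, the false-positive rate in the drug's favour is 2.5% and nothing changes. It becomes 5% only if one-sided inference is applied at 0.05 against SAP 8.5. The stated power fits either sidedness, so it cannot decide the matter.

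The Estimand 2 p-value is a separate drafting gap: undefined as to sign, pointing at the wrong tail if read literally on the SAP's scale, and inconsistent with protocol 10.4.5. It matters only if the missing-data trigger is met.

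**What to change.** - **SAP 2.5:** replace the sentence with a statement that hypotheses and testing are two-sided at alpha = 0.05, and that superiority is claimed only if the difference, tanfanercept minus placebo, is negative, as in SAP 8.5.
- **SAP 2.6, Estimand 2:** define the p-value as the proportion of permutations whose absolute effect is at least as large as the absolute observed effect.

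The cost is one sentence in each section. Sample size and stated power do not change, and both sentences then agree with SAP 8.5 and the protocol.

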2.6 Estimands

The primary analysis of the primary endpoints will use the Intent-to-Treat (ITT) population for the primary endpoints of Change from Baseline (CFB) of CCSS at Day 57 ± 3 and CFB of EDS-VAS at Day 57 ± 3 , and the primary analysis will be executed using mixed model repeated measures (MMRM) with multiple imputation methodology using the following estimand:

Estimand 1:

- Population:
 - ITT population
- Endpoints:
 - CFB in CCSS in the study eye at Day 57 ± 3 in the ITT population
 - CFB in EDS from VAS at Day 57 ± 3 in the ITT population
- Intercurrent events:
 - Discontinuation of study medications is ignored. Measures obtained after discontinuation of study medication will be analyzed. [treatment policy strategy]
 - Non-optimal compliance is ignored. Measures will be analyzed regardless of treatment compliance. [treatment policy strategy]
 - Use of prohibited concomitant medications is ignored. Measures obtained after use of prohibited concomitant medications will be analyzed. [treatment policy strategy]
 - Withdrawal due to lack of efficacy or adverse events: Missing values assumed to be missing not at random will be multiply imputed using placebo group-based PMM imputation. [hypothetical strategy]
 - Missing data with withdrawal or withdrawal due to reasons other than lack of efficacy or adverse events: Missing values assumed to be missing at random will be multiply imputed using randomized treatment group-based MCMC imputation. [hypothetical strategy]
- Population-level summary:
 - Difference in the mean CFB in CCSS in the study eye at Day 57 ± 3 between Tanfanercept and placebo in the ITT population.
 - Difference in the mean CFB in EDS (VAS) at Day 57 ± 3 between Tanfanercept and placebo in the ITT population.

If the rate of missing data for EDS-VAS is imbalanced between treatment groups (demonstrated by Fisher's exact test with a p-value of <0.05) and the rate of missing data for EDS-VAS is $\geq 10\%$ in all subjects, then the primary analyses will utilize the ITT population using the permutation test with trimmed means methodology, as detailed in Estimand 2.

Estimand 2:

- Population:
 - ITT population
- Endpoint:
 - CFB in CCSS in the study eye at Day 57 ± 3 in the ITT population
 - CFB in EDS from VAS at Day 57 ± 3 in the ITT population
- Intercurrent event:
 - Discontinuation of study medications is ignored. Measures obtained after discontinuation of study medication will be analyzed. [treatment policy strategy]
 - Non-optimal compliance is ignored. Measures will be analyzed regardless of treatment compliance. [treatment policy strategy]
 - Use of prohibited concomitant medications is ignored. Measures obtained after use of prohibited concomitant medications will be analyzed. [treatment policy strategy]
 - Withdrawal or missed assessments for any reason. Missing values will be removed, following the trimmed means methodology laid out in Permutt T, Li F. [hypothetical strategy]. The trimmed means strategy is as follows:
 - Using an analysis of covariance (ANCOVA), a linear model is fit to the data with treatment as factor and baseline value as covariate. The beta coefficient for treatment is discarded and only the Y (outcome) value, the beta coefficient for baseline score, and X (baseline score) are considered. $Y - \beta(X)$ is then calculated for each subject for the purpose of ranking.
 - Next, the proportions of subjects with missing values in the control and treatment arms are identified. The greater proportion of the two arms is then used as the percentile floor in which observations must be better. Those observations that are not better than the floor are trimmed (removed). Missing values are included in the calculation of the percentile floor value as values worse than the percentile.
 - After trimming is done, MMRM is used on the two analysis sets to find an observed treatment effect. The MMRM model will be based on the final model as described in [Section 13.1.1](#). To determine the p-value and 95% CI, 10,000 permutations of the data will be run and the trimming methodology will be repeated. The number of permutation datasets that result in an effect size greater than the observed effect size divided by the number of permutations will be the p-value. The 95% CI will be calculated using the 2.5th and 97.5th percentiles of the permutation distribution.
- Population-level summary:
 - Difference in the mean CFB in EDS-VAS at Day 57 ± 3 between Tanfanercept and placebo in the ITT population.

3. Study Design and Procedures

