5.5 Withdrawal Criteria

Subjects may withdraw their consent to participate in the study at any time without prejudice. The Investigator must withdraw from the study any subject who requests to be withdrawn. A subject's participation in the study may be discontinued at any time at the discretion of the Investigator and/or Sponsor and in accordance with his/her clinical judgment. However, it is encouraged that the Investigator contact the Sponsor, when possible, to discuss possible reasons for discontinuation prior to withdrawing a subject from the study. Tests and evaluations listed for the termination visit should be carried out as outlined in [Section 8.4.3](#).

Sponsor and Ora must be notified of all subject withdrawals as soon as possible. Sponsor also reserves the right to discontinue the study at any time for either clinical or administrative reasons.

Reasons for which a subject may be withdrawn from the study by the Investigator or the Sponsor may include, but are not limited to, the following:

- Subject experiences a serious or intolerable AE
- Subject requires medication prohibited by the protocol
- Subject does not adhere to study requirements specified in the protocol
- Subject was erroneously admitted into the study or does not meet entry criteria
- Subject is lost to follow-up
- Subject becomes pregnant
- Sponsor decision

If a subject fails to return for scheduled visits, a documented effort must be made to determine the reason. If the subject cannot be reached by telephone after two attempts, a certified letter should be sent to the subject (or the subject's legally authorized representative, if appropriate) requesting contact with the Investigator. This information should be recorded in the study records.

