8.4.11 Early Termination Visit

In the case when a subject discontinues from the study, every effort should be made by the site to conduct an early termination visit in order to monitor subject safety. All procedures performed at an early termination visit will be recorded in the source documents and on the Early Termination Visit eCRF.

- Study Drug Collection
- Monitoring and Query of AEs
- Record all Changes in Concomitant Medications
- Urine Pregnancy Test (for females of childbearing potential)
- Ora Calibra® Ocular Discomfort Scale
- Ora Calibra® Ocular Discomfort & 4-Symptom Questionnaire

- VAS
- OSDI[®]
- BCVA Utilizing an ETDRS Chart
- Slit-Lamp Biomicroscopy
- Conjunctival Redness
- TFBUT
- Corneal and Conjunctival Staining (fluorescein)
- Corneal and Conjunctival Staining (lissamine green)
- Schirmer's Test
- Intraocular Pressure
- Dilated Fundoscopy
- Blood Sampling for Immunogenicity Testing
- Any other assessments needed in the judgment of the investigator
- [REDACTED]

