9.4 Procedures for Unmasking (if applicable)

All subjects, investigators, and study personnel involved with the conduct of the study will be masked with regard to treatment assignments. When medically necessary, the investigator may need to determine what treatment arm has been assigned to a subject. When possible (i.e., in non-emergent situations), Ora and Sponsor should be notified before unmasking a subject's study drug treatment. The unmasked subject will be discontinued from the study.

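### The treatment-policy strategy for study-drug discontinuation and prohibited medication has no matching pathway for off-drug subjects to be assessed through Day 57

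*SAP*

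**What the plan says.** **Estimands.** SAP 2.6 and Protocol 10.4.5 apply the same strategy in Estimands 1 and 2. On stopping study drug: "Measures obtained after discontinuation of study medication will be analyzed". On prohibited medication: "Measures obtained after use of prohibited concomitant medications will be analyzed". Both are tagged treatment policy.

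**Missing values under Estimand 1.** Separate rows cover withdrawal and missing data. After withdrawal for lack of efficacy or adverse events, values "will be multiply imputed using placebo group-based PMM imputation. [hypothetical strategy". After withdrawal for any other reason, or when data are missing without withdrawal, values "will be multiply imputed using randomized treatment group-based MCMC imputation. [hypothetical strategy".

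**Conduct.**
- Protocol 8.6.1 and 8.6.2 recognise completed subjects and subjects discontinued from the study. SAP 9.1 tabulates the same two states.
- SAP 12.1 and 12.2 run expected doses and exposure to the date of study completion or discontinuation, not to the last dose.
- Protocol 8.4.11: "In the case when a subject discontinues from the study, every effort should be made by the site to conduct an early termination visit". Its stated purpose is safety monitoring. Protocol Section 4 asks early terminators for safety assessments before they start another dry eye therapy.
- Protocol 5.5 gives a list headed "Reasons for which a subject may be withdrawn from the study by the Investigator or the Sponsor", and one entry is "Subject requires medication prohibited by the protocol".
- Protocol 9.4, on unmasking: "The unmasked subject will be discontinued from the study". Protocol 9.1 likewise requires study exit for pregnancy.

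**The concern.** A treatment-policy strategy needs the Week 8 outcome after the intercurrent event. A subject who stops study drug can supply it only by continuing to attend, and the conduct sections provide no such status. If stopping drug becomes leaving the study, the value is missing and the withdrawal rows take over. Which strategy applies then depends on an administrative decision, not on the event.

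The direction matters. Own-arm imputation fills an active-arm subject's Week 8 value from active-arm subjects who remained. The MCMC code in SAP Appendix 1 runs by treatment on baseline and Visits 3 to 6, with no indicator for being off drug. If benefit fades after stopping, these imputed values are too good in the active arm, and the estimated difference leans towards the drug on both CCSS and EDS.

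**Working it through.** **1. Which data survive each event**

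| Event | Subject stays in the study | Subject leaves the study |
|---|---|---|
| Stops study drug | Value analysed, but no status or visit pathway is described | One termination visit; Week 8 imputed |
| Uses prohibited medication | Value analysed; SAP 9.2 has a deviation category for it | Withdrawal is discretionary (5.5); Week 8 imputed from own arm, since the reason is neither adverse event nor lack of efficacy |
| Poor compliance | Value analysed; Protocol 8.5 calls for re-education | Not implied by 8.5 |

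The gap is clearest for stopping drug and partial for prohibited medication. For poor compliance the strategy is workable as written. One case escapes imputation after exit: SAP Table 1 sets the Visit 6 analysis window at Day 44 to Day 60, and the termination visit includes VAS and fluorescein staining, so a termination visit on those days can serve as Visit 6.

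**2. Planned amount of missing data**

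Protocol 10.3 assumes 10% dropout: 150 × 0.90 = 135 completers per arm, which reproduces its figure. That leaves 15 per arm (30 of 300) without Day 57 data. At the 130 per arm in SAP Section 5, 10% is 13 per arm (26 of 260). Neither document gives a rate for drug discontinuation or prohibited-medication use, so the share of post-event data that is lost cannot be calculated.

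**3. Planning effect, for scale only**

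The difference and SD are redacted. The standardized effect *d* giving 99.4% power at 135 per arm, two-sided 0.05, is, by the normal approximation,

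*d* = (1.960 + 2.512) / √(135/2) = 4.472 / 8.216 = 0.544.

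The noncentral t gives 0.546. At 119 per arm this returns 98.7%, matching SAP Section 5.

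**4. Illustration for Estimand 1**

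Assumptions, none of them from the documents except the 10%:
- dropout is 10%, and every dropout is off drug;
- all benefit is lost off drug;
- own-arm imputation restores the full benefit, and placebo-based imputation removes it;
- *s* is the share of dropouts imputed from their own arm.

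Treatment-policy effect = *d* × 0.90 = 0.546 × 0.90 = 0.491 SD.

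Estimated effect = *d* × [1 − 0.10 × (1 − *s*)].

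Overstatement = [1 − 0.10 × (1 − *s*)] / 0.90 − 1.

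| *s* | Estimated effect (SD) | Overstatement |
|---|---|---|
| 25% | 0.546 × 0.925 = 0.505 | 0.925/0.90 − 1 = 2.8% |
| 50% | 0.546 × 0.950 = 0.519 | 0.950/0.90 − 1 = 5.6% |
| 75% | 0.546 × 0.975 = 0.532 | 0.975/0.90 − 1 = 8.3% |
| 100% (ceiling) | 0.546 | 1/0.90 − 1 = 11.1% |

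The percentages do not depend on *d*. The error is multiplicative: in this illustration it enlarges a real effect and does not create one where there is none. It does not apply to Estimand 2, where missing values are trimmed.

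**The case against.** The strongest reply is that silence is not contradiction, and much of it stands.

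- A reader might infer that the protocol equates stopping drug or using prohibited medication with leaving the study. No sentence says so. Protocol 5.5 and 8.6.2 are permissive, SAP 9.2 counts prohibited-medication use and non-compliance as deviations, and SAP 15.1 counts treatment discontinuation due to an adverse event. Some such subjects will stay and be measured.
- A reader might infer that the estimand is mislabelled throughout. It is not: the withdrawal rows are separate and already tagged hypothetical.
- A reader might infer that most post-event data will be missing, or that the 11% ceiling is the expected bias. The documents give no rate to support the first. The second ignores placebo-based imputation after withdrawal for adverse events or lack of efficacy.
- Mandatory exit on unmasking is weak evidence, because unmasking is not one of the treatment-policy events.
- Protocol 10.4.3 and SAP 8.2 already list placebo-based PMM for all missing data, which tests the feared scenario. SAP 8.2 adds a tipping-point analysis, worded as optional. Termination results before Day 44 can fall in the Visit 3 to 5 windows and inform the imputation.
- Some dropouts will be lost to follow-up or withdraw consent, and better follow-up rules would not recover them.

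What does not stand is the suggestion that this supplies the missing pathway. A deviation category or an adverse-event listing does not schedule a Week 8 assessment for someone off drug. A sensitivity analysis tests the consequence of lost data; it does not restore the data the primary estimand calls for.

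**Conclusion.** The point holds as a mismatch between estimand and conduct. It is not a flat contradiction. Treatment policy is specified for stopping study drug and for prohibited medication, but in the text that can be read there is no route for staying in assessments to Day 57 off drug. Some of the protocol is redacted, including Section 8.3, so this rests on the visible text. Following the plan as written can lose values that its primary estimand needs, and under Estimand 1 some of these are replaced from the subject's own arm.

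The likely direction favours the drug. The size is modest and uncertain: about 3% to 8% of the treatment-policy effect for *s* between 25% and 75%, or roughly 0.01 to 0.04 SD on the back-solved planning effect, with 11% (0.05 SD) as the ceiling. These figures rest on the assumptions listed above. Less than full loss of benefit off drug would make them smaller. This is worth correcting because the remedy is cheap; it does not by itself undermine the primary test.

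**What to change.** 1. In Protocol 5.5, 8.4.11 and 8.6.2 and SAP 9.1, record study-drug discontinuation, with its date and reason, separately from withdrawal from the study.
2. In the same protocol sections, state that subjects who stop study drug without withdrawing consent keep the already scheduled CCSS and VAS assessments through Visit 6. This leaves unchanged who stops treatment and when.
3. SAP Section 5 reports that 260 subjects were already randomized, so missed visits cannot be recovered for those who have left. For them, state in SAP 2.6, before unmasking, that post-exit values are handled under the hypothetical strategy. Use the planned placebo-based PMM analysis for all missing data as the check on the primary result.

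The cost is protocol and SAP wording and one eCRF field; the visits already exist in the schedule. The downside is the site effort needed to keep off-drug subjects attending. The change will not recover subjects who are lost to follow-up or withdraw consent.
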